#### **14.5.1 Recording and reporting pregnancies/suspected pregnancies**

Pregnancies and suspected pregnancies (including a positive pregnancy test regardless of age or disease status) in a female participant must be reported throughout the study and for 3 months after stopping treatment. Pregnancies and suspected pregnancies (including a positive pregnancy test regardless of age or disease status) in a male participant's partner must be reported throughout the study and for 3 months after stopping treatment. Pregnancies must be reported using the electronic Pregnancy eCRF within 24 hours of the research staff becoming aware of the event.

Because the effect of ibrutinib on sperm is unknown, pregnancies in partners of male participants exposed to ibrutinib will be reported within 24 hours of the knowledge of the event using the Serious Adverse Event eCRF. Depending on local legislation, this may require prior consent of the partner.

**Contact details for queries relating to pregnancies/suspected pregnancies**

**Email: [[contact]](mailto:[contact])**

The CTRU will report the pregnancy or suspected pregnancy to relevant pharmaceutical companies as required on the same working day that Sponsor is made aware and will follow the pregnancy up to outcome.

Pregnant participants must be followed until the end of their pregnancy and the CTRU must be notified of the outcome of the pregnancy (including false-positive pregnancy tests) within 24 hours of this information being known. If a pregnancy occurs in a male participant's partner, details of the pregnancy will still be collected where possible and the outcome of the pregnancy must be notified to the CTRU.

The outcome of any pregnancy which qualifies as a SAE (i.e. spontaneous or therapeutic abortion, foetal and neonatal death, or congenital abnormalities – including those detected in an aborted foetus), birth defects, or the death of an infant which occurs in connection with in utero exposure to the study drugs must be reported to the CTRU as a SAE in accordance with Section 14.4.

## **14.6 Pharmacovigilance responsibilities**

### **14.6.1 Local Principal Investigator**

- Checking for AEs/ARs, SAEs and AEoSI during treatment/follow up's;
- Ensuring that AEs and ARs are recorded and reported to the CTRU in line with the requirements of the protocol.
- Using medical judgement in assigning seriousness and causality to SAEs/SUSARs, using the RSI approved for the trial;
- To ensure that the trial team are using the correct version of the safety reference documents;
- To ensure all SAEs, SARs (including SUSARs) and AEoSIs are recorded and reported to the CTRU within 24 hours of becoming aware and to provide further key follow up information within 24 hours. To ensure that reported events are chased with the CTRU if a confirmation of receipt is not received within 2 days of reporting.
- To report SAEs to local committees in line with local arrangements.
- In the case of pregnancy, to ensure that treatment is stopped immediately (in female participants) and the pregnancy is reported to the CTRU within 24 hours of becoming aware.

### **14.6.2 Clinical Trials Research Unit, University of Leeds (CTRU)**

- Identifying at the beginning of the study the information in the SmPC (or IB) that will be used as the RSI for pharmacovigilance reporting.
- Central data collection and verification of AEs, ARs, SAEs, SARs, SUSARs and AEoSIs according to the trial protocol onto a MACRO database according to MedDRA.
- Using the RSI to assign expectedness of all SAEs
- Reporting safety information to the CI, delegate or independent clinical reviewer for the ongoing assessment of the risk / benefit ratio.
- Notifying the local investigator of any event reported from their site that is assessed by the Chief Investigator (or delegate) as unexpected.
- Reporting safety information to the independent oversight committees identified for the trial Data Monitoring & Ethics Committee (DMEC) and / or Trial Steering Committee (TSC).
- Expedited reporting of SUSARs to the Competent Authority (Medicines and Healthcare Products Regulatory Agency (MHRA) in UK), REC and Sponsor within required timelines.
- Notifying Investigators of SUSARs that occur within the trial.
- Notifying PIs at sites, the Sponsor, REC and MHRA/relevant regulatory authority of findings that could adversely affect the health of participants, impact on the conduct of the trial, or alter the authority's authorisation of the trial.
- Reporting events to collaborating pharmaceutical company in accordance with the trial contracts
- Checking for updates to the RSI (annually as a minimum) and communicating changes to the CI for reassessment of the risk benefit ratio.
- Notifying PIs of updates to the RSI.

- Communicating changes associated with a change in the risk benefit ratio to sites via a substantial amendment.
- Preparing standard tables and other relevant information for the Developmental Safety Update Report (DSUR) in collaboration with the CI and ensuring timely submission to the MHRA, REC and relevant pharmaceutical companies. The DSUR will be prepared annually.
- Providing periodic safety reports to the DMEC
- Monitoring site's compliance with safety reporting procedures and timelines.

#### **14.6.3 Chief Investigator (or delegated member of the TMG)**

- Using medical judgement to assign causality of SAEs where it has not been possible to obtain local assessment
- To review all SAEs and SARs
- To review all events assessed as SUSARs
- Preparing the clinical sections, and final sign-off of the DSUR

#### **14.6.4 Pharmaceutical companies**

- Inform the CTRU/CI of any new information, which becomes available during the course of the study, which may affect the overall safety profile of the study drug.

#### **14.6.5 Data Monitoring and Ethics Committee (DMEC)**

- In accordance with the trial the DMEC charter, periodically reviewing safety data to determine patterns and trends of events, or to identify safety issues, which would not be apparent on an individual case basis.
- Reviewing results from interim analyses for early efficacy (one for each of the randomisations).

#### **14.6.6 Trial Steering Committee (TSC)**

- In accordance with the trial Terms of Reference for the TSC, provide advice on all appropriate aspects of the trial, including trial progress, adherence to the protocol, and participant safety and liaising with the DMEC regarding safety issues.

### **14.7 Safety Monitoring Plan**

Refer to Appendix 10.

# 15 QUALITY OF LIFE AND HEALTH ECONOMICS

---

## 15.1 Quality of Life studies

Quality of life will be assessed in participants in the randomisation pathway, who are able to read and complete the quality of life questionnaires using validated instruments completed at appropriate and specified timepoints throughout the trial. The QLQ-CLL (latest version validated at the time of trial opening), a CLL specific module, EORTC QLQ-C30, and EQ-5D-5L will be used to assess quality of life during the trial. The EORTC QLQ-C30 is a multi-dimensional tool for participants with cancer that addresses aspects of participants' functioning and symptoms as well as their overall quality of life. The EORTC-QLQ-CLL aims to specifically address the health-related quality of life of CLL patients. EQ-5D-5L is a generic multidimensional to measure a patient's general health.

QoL and health economics questionnaires can be completed on paper CRFs or electronically, in line with the participants preference. These can be completed at clinic visits or if a clinic visit is not possible, the participant can complete this at home, at the time-points detailed in Section 13 and Appendix 4.

Participants completing paper questionnaires during clinic visits will be given an envelope to seal their questionnaires in before returning to their clinical team in order to preserve the confidentiality of their answers. The clinical team should post the paper questionnaires (within the sealed envelope) to the CTRU. If questionnaires have been posted to the participant for completion at home, an addressed envelope should be provided so that the questionnaires can be posted directly back to the STATIC team at the CTRU. The clinical team should not read, review or photocopy the questionnaires.

Participants will continue to be asked to complete questionnaires at all timepoints specified (Section 13 and Appendix 4) regardless of whether previous questionnaires have been completed, unless they express a wish to withdraw consent for this part of the study.

## 15.2 Health Economics

Data to enable the economic evaluation will come from responses to EQ-5D-5L, EORTC QLQ-C30 and health care resource use measures. We will supplement this with a Hospital Episode Statistics data request.

## 16 CRITERIA OF RESPONSE

---

Active disease and response to treatment will be assessed according to 2018 iwCLL criteria (Appendix 1).

The local clinician will provide an assessment of response in line with the response criteria as required by the schedule of investigations (see Appendix 4).

# 17 ENDPOINTS

---

## 17.1 Primary Endpoint

The primary endpoint will be evaluated in the Randomisation Pathway only.

- Time to Treatment Strategy Failure

## 17.2 Secondary Endpoints

All secondary endpoints will be evaluated for participants in the Randomisation Pathway, given the relevant consent. For the Clinical Need Cohort, only the following will be assessed: overall survival, toxicity and tolerability, time to next treatment and response to next treatment.

- Overall Survival
- Toxicity and Tolerability
- Cost Effectiveness of the Intermittent Treatment Strategy
- Quality of Life
- Summative treatment-free Interval
- Response to re-treatment in the intermittent arm
- Time to next treatment for CLL
- Response to next treatment for CLL
- Rate of Resistance Mutation between Trial-Arms
- Evolution of Resistant Sub-Clones

## 17.3 Exploratory Endpoints

All exploratory endpoints will be evaluated for participants in the Randomisation Pathway, given the relevant consent. For the Clinical Need Cohort, only the following will be assessed: Assessment of response to vaccines and on infectious complications.

- Analysis of the cause of ibrutinib resistance where BTK mutations are not found
- Identification of predictors for early progression of CLL after pausing ibrutinib
- Study of CLL clonal evolution in patients treated with ibrutinib
- Assessment of response to vaccines and on infectious complications

## 17.4 Derivation of Endpoints

### 17.4.1 Time to Treatment Strategy Failure

Time to treatment strategy failure is defined as the time from randomisation to time of treatment strategy failure. Treatment strategy failure is defined as the first documented instance of active disease that does not respond to treatment, or death from any cause. If a participant reaches active disease whilst on a break and they continue to meet this criteria whilst on subsequent ibrutinib treatment, then the time of the event is when they first met the criteria for active disease. Individuals who are lost to follow-up, withdraw from all follow-up or continuing with their treatment strategy at the time of analysis will be censored at the date of last assessment. Participants who transfer to an alternate BTK inhibitor without experiencing active disease will be censored at their last assessment pre-transfer.

#### **17.4.2 Overall Survival**

Overall survival is defined as the time from randomisation to the time of death from any cause. Individuals who are lost to follow-up or still alive at the time of analysis will be censored at their last known date to be alive.

For the Clinical Need Cohort, this will be time from registration to the time of death from any cause.

#### **17.4.3 Toxicity and Tolerability**

Toxicity and tolerability will be reported based on the adverse events, as graded by CTCAE V5.0 and determined by routine clinical assessments at each centre. SAEs will be reported according to MedDRA System Organ Class.

For the Clinical Need Cohort this endpoint will be defined as above.

#### **17.4.4 The Cost Effectiveness of the Intermittent Treatment Strategy**

Cost-effectiveness is defined as a cost per incremental QALY below £20,000 and/or a positive incremental net monetary benefit. The cost-effectiveness of treatment options will be evaluated with respect to this criteria. Details of all analyses will be detailed in a separate health economics analysis plan.

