## 18.1 Sample Size

As the primary endpoint will be evaluated for the Randomisation Pathway the sample size and recruitment rate calculations are based on participants entering this pathway.

In relapsed/refractory patients, the median PFS on ibrutinib is almost 4 years [7]. In treatment naive patients, the median PFS is estimated to be approximately 10 years [6]. We expect to be able to recruit ~45% of participants from FLAIR and ~55% from relapsed/refractory patients. We assume that PFS will be strongly related to the primary endpoint: time to treatment strategy failure. Assuming exponential distributions leading to a hyperexponential distribution, these medians combine to produce an overall median PFS of 5.84 years. We use PFS here as a surrogate for time-to-treatment strategy failure.

With a one-sided alpha of 2.5%, 80% power and allowing for 5% dropout, to detect a non-inferiority hazard ratio (HR) upper bound of 1.33 would require 379 events (using the continuous treatment arm as the reference). Accounting for those participants who will be lost-to-follow-up 800 patients (approximately 140/year) are planned to be randomised over a 6 year period, with the required number of events expected at approximately 3 years after the close of recruitment.

The highest HR point estimate that would lead to a result of non-inferiority is 1.08, based on a 95% confidence interval of (0.89, 1.33). This corresponds to the intermittent treatment strategy having an 8% extra risk of relapsing, or equivalently a 2.7% decrease in 5-year PFS probabilities (55.2% to 52.5%), with a range of a 9.3% decrease to a 3.3% increase. This reduction in PFS agreed to be clinically acceptable with the National Cancer Research Institute (NCRI) CLL subgroup, because of expected reduction in toxicity, increase in QoL, and the substantial potential for health care resource savings. In addition, there are good salvage therapies on progression, such as venetoclax which is approved for patients failing ibrutinib in the NHS, so a small impact on PFS would not be likely to translate to a difference in overall survival (OS).

We believe it is very likely that the intermittent strategy will actually be superior to continuous treatment in terms of PFS, because the treatment breaks may well delay the time to emergence of drug resistance (18, 19) as well as reducing long-term toxicities (20). If the experimental strategy is actually 5% better, the power increases to 90%.

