### **19.4.3 The Cost Effectiveness of the Intermittent Treatment Strategy**

An economic evaluation of continuous versus intermittent treatment will be conducted following the NICE reference case with the primary outcome being incremental cost per quality-adjusted life year (QALY) gained. The perspective will be that of the health care and personal social service provider. Utility values will be generated during the trial using the EQ-5D-5L (23) and EORTC-8D (24). Currently, NICE advise the use of a published (EQ-5D-5L to EQ-5D-3L) mapping algorithm to generate the utility index from the EQ-5D-5L (25, 26). However, a new valuation study is on-going (27) and we will use the new UK valuation tariff when this is available, providing the results are valid and robust. QALYs will be generated using an area under the curve approach between adjacent EQ-5D-5L completions (or death). These will be based on the EORTC-8D in a supplementary analysis.

Costs will be based on patient-completed resource use questionnaires (for primary, community and social care) and NHS digital data (for secondary care). The questionnaires will be completed at baseline and every subsequent follow-up. Therapy use will be captured in the CRFs. Unit costs will be taken from resources such as NHS reference costs, Personal Social Services Research Unit (PSSRU) report, electronic market information tool (eMIT) and British National Formulary (BNF). We will use the prevailing drug list prices at the time of analysis.

In the trial analysis, regression models will be used to adjust for baseline imbalance and account for cost-QALY correlations. Where appropriate, we will mirror the statistical team approach to incorporating control variables and adjust for the specified stratification factors (excluding centre). We will assess the type and degree of missing data and evaluate whether the assumption of missing at random (MAR) holds (28). If that is the case, multiple imputation will be used to impute missing data. Should MAR not hold we will explore the impact of alternative assumptions (29). We will report incremental cost-effectiveness ratios (ICERs) (30) at trial end however the primary end-point will be based on lifetime expected costs and outcomes generated from a decision analytic model.

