A decision-analytic model being developed in FLAIR will allow the extrapolation of costs and consequences of the treatment strategies over a lifetime horizon. The FLAIR decision model is a Markov model with health states based around CLL response criteria. The final model will be agreed with patient and clinician collaboration. Parameter values will be derived from the proposed trial and other relevant datasets (such as FLAIR and ARCTIC (ISRCTN16544962)) and reviews of the literature. Survival will be extrapolated using parametric survival curves selected using guidance from the NICE Decision Support Unit (31). Incremental cost effectiveness ratios (ICERs) will be generated over a lifetime horizon in reference to the £20,000-£30,000 per QALY willingness to pay threshold. We will conduct extensive deterministic sensitivity analyses and capture total parameter uncertainty using a

probabilistic sensitivity analyses. Results will be represented as cost-effectiveness acceptability curves (32) and net monetary benefit distributions.

As part of the interim analysis, we will use the decision model to explore the cost-effectiveness of treatment breaks and generate value of information estimates to inform study continuation decisions (33). Costs and benefits post 12 months will be discounted at a rate of 3.5% per annum as per NICE guidance. NICE is currently updating the guidance for technology appraisals and we will review the planned methods stated here taking into consideration the updated guidance when published.

A full health economics analysis plan (HEAP) will be written before any analysis is undertaken.

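### The cost-effectiveness definition in 17.4.4 ignores the sign of the QALY difference, so its ICER limb points the wrong way if pausing loses QALYs, and 'and/or' does not settle the conflict

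*Protocol*

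**What the plan says.** Section 17.4.4 of the protocol fixes the criterion: "Cost-effectiveness is defined as a cost per incremental QALY below £20,000 and/or a positive incremental net monetary benefit". It then makes the criterion operative: "The cost-effectiveness of treatment options will be evaluated with respect to this criteria". The section puts no condition on the direction of the cost or QALY difference, does not choose between 'and' and 'or', and names no threshold for the net benefit. Analysis details are deferred: "Details of all analyses will be detailed in a separate health economics analysis plan".

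Section 19.4.3 describes the economic evaluation as having "the primary outcome being incremental cost per quality-adjusted life year (QALY) gained". Lifetime ICERs are to be read "in reference to the £20,000-£30,000 per QALY willingness to pay threshold". On presentation it says: "Results will be represented as cost-effectiveness acceptability curves (32) and net monetary benefit distributions". It does not restate or amend the definition in 17.4.4.

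Section 18.1 explains why a small loss of progression-free survival (PFS) was judged acceptable. The reasons include lower toxicity, better quality of life and "the substantial potential for health care resource savings".

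**The concern.** An ICER is a ratio, and its meaning depends on the signs of its two parts. When a strategy costs more and gains QALYs, a low ICER is good. When it saves money and loses QALYs, the ICER is the saving per QALY given up, and a low value is bad. A rule that asks only whether the ICER is below a fixed figure treats both cases alike.

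This matters more than usual for a trial of treatment pauses. Section 18.1 accepts a small efficacy loss partly in return for savings, so a cheaper strategy with some health loss is a result the economic rule should be able to judge. With 'and/or' left open, the verdict in that region would depend on which connective is chosen, possibly after the results are known. At stake is the prespecified conclusion on a secondary endpoint that bears directly on an NHS adoption decision.

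**Working it through.** **Inputs.** The £20,000 cut-off and the two limbs come from 17.4.4, and the £20,000-£30,000 range from 19.4.3. The criterion is a definition, so there is no calculated figure of the plan to reproduce. The documents give no drug cost and no expected QALY difference, so every cost and QALY value below is an assumption chosen to illustrate.

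**Formulas.** Let ΔC and ΔQ be the cost and QALY differences, pausing minus continuous, and λ the value of a QALY.

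- ICER = ΔC / ΔQ
- Incremental net monetary benefit (INMB) = λΔQ − ΔC

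**Algebra.** INMB > 0 means ΔC < λΔQ. Divide by ΔQ:

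- if ΔQ > 0, this becomes ICER < λ, and the limbs agree at the same λ;
- if ΔQ < 0, the inequality reverses to ICER > λ, and the ICER limb in 17.4.4 points the wrong way.

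With ΔC < 0, ΔQ < 0 and λ = £20,000, exactly one limb is met in every case except exact equality, where neither is. So 'or' passes every such result and 'and' passes none. A numerical check with one million random pairs in that quadrant (savings up to £40,000, losses up to 2 QALYs) gave the same answer: the limbs agreed in 0% of pairs, 'or' passed 100% and 'and' passed 0%.

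**Examples at λ = £20,000.**

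| ΔC | ΔQ | ICER | INMB | ICER limb | INMB limb | 'or' | 'and' |
|---|---|---|---|---|---|---|---|
| +£10,000 | +1.0 | £10,000 | 20,000 − 10,000 = +£10,000 | met | met | right | right |
| −£10,000 | +1.0 | −£10,000 | 20,000 + 10,000 = +£30,000 | met | met | right | right |
| −£10,000 | −1.0 | £10,000 | −20,000 + 10,000 = −£10,000 | met | not met | wrongly passes | right |
| −£19,000 | −1.0 | £19,000 | −20,000 + 19,000 = −£1,000 | met | not met | wrongly passes | right |
| −£21,000 | −1.0 | £21,000 | −20,000 + 21,000 = +£1,000 | not met | met | right | wrongly fails |
| −£50,000 | −0.5 | £100,000 | −10,000 + 50,000 = +£40,000 | not met | met | right | wrongly fails |
| +£5,000 | −0.5 | −£10,000 | −10,000 − 5,000 = −£15,000 | met | not met | wrongly passes | right |

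The last row is a dominated strategy: dearer and worse. Its ICER is negative and so literally below £20,000.

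**Threshold.** Section 17.4.4 gives no λ for its net benefit limb. Take +£25,000 with +1.0 QALY. The ICER limb fails. INMB is 20,000 − 25,000 = −£5,000 at the lower end of the range in 19.4.3, and 30,000 − 25,000 = +£5,000 at the upper end. The verdict turns on a value the definition leaves out.

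**The case against.** The strongest reply is that the net benefit limb is correct in every quadrant, that 19.4.3 already commits to reporting net benefit distributions and acceptability curves, and that a separate health economics plan, not shown here, will hold the detail. A health economist would read the ICER by quadrant without being told. It can also be said that cost per QALY gained presupposes a gain, so the dominated example is a strained reading. Much of this stands: the right measure will be reported, and the practical harm is limited. It does not rescue the definition. Section 17.4.4 defers details of the analyses, but it states the criterion itself, and nothing in 19.4.3 corrects it. Reading the ICER by quadrant would mean setting the written rule aside.

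A reader might also infer more than the documents support:

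- *That the rule is wrong whenever pausing saves money and loses QALYs.* It is not. 'Or' errs only below £20,000 saved per QALY lost, and 'and' errs only above it. A large saving with a small loss is judged correctly under 'or'.
- *That such a result is likely.* The protocol expects otherwise. Section 7.3.1 hypothesises better quality of life, and 18.1 considers superiority in PFS very likely and an effect on overall survival unlikely. Cheaper with more QALYs is the expected case, and both limbs agree there.
- *That the design accepts a 33% higher failure hazard.* In 18.1, 1.33 is the limit for the upper confidence bound. The highest passing point estimate is stated as 1.08, a 2.7-point fall in 5-year PFS. The margin concerns strategy failure, not QALYs.
- *That the two thresholds contradict each other.* £20,000 is the lower end of the range in 19.4.3. The two sections need aligning, but they do not conflict.

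**Conclusion.** The point holds as a fault in a stated decision rule. When QALYs are lost, the ICER limb in 17.4.4 is reversed, and 'and/or' leaves open which limb prevails. In the cost-saving, QALY-losing quadrant at £20,000 per QALY, the rule cannot discriminate under either reading: one passes everything and the other passes nothing. Read literally as 'or', it also passes a dominated strategy.

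The algebra needs no assumption beyond using £20,000 as the value of a QALY in the net benefit limb, which 17.4.4 implies but does not state. How probable the affected region is cannot be computed from the documents; it is plausible but not predicted. The consequence is confined to a secondary economic endpoint. The change should be made, but nothing in the primary analysis depends on it.

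**What to change.** In 17.4.4, define cost-effectiveness solely as incremental net monetary benefit greater than zero at £20,000 per QALY, the figure the section already uses, and delete the ICER limb together with 'and/or'. Report the ICER descriptively with the quadrant in which it falls. In 19.4.3, add a sentence saying how the £20,000-£30,000 range relates to that decision threshold, for example with £30,000 as a sensitivity value. Carry the same wording into the health economics analysis plan.

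The cost is about one sentence in each section. Net benefit is already planned, so no new data, analysis or participants are needed.
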